#### **Tissue sample from an undiagnosed suspicious lesion:**

Using a scalpel, bisect the tissue sample first, then carefully separate the epithelium from the subcutaneous tissue on one of the halves and place it in the RNAlater cryovial labeled “Tumor (Baseline)”. Place the other half in a container of 10% formalin and submit for clinical histopathology per standard of care guidelines.

Process the RNAlater samples in accordance with the instructions in section 10.2.2

Samples in formalin will be paraffin-embedded and stored en bloc until the request for slides to be cut is issued.

**At the End of Study Visit:** Two 4 mm tissue samples will again be obtained:

- One of visually normal appearing mucosa
- One of the oral/oropharyngeal tumor

Half of each sample will be processed for RNA-seq analysis. The other half will be formalin-fixed and paraffin-embedded.

**The process for obtaining these samples will depend on whether or not the samples are obtained during surgical excision of the tumor**

Have available:

- A 4 mm biopsy punch (if the lesion is not accessible by biopsy punch, alternative tools sufficient to yield a 4 mm piece of tissue with the epithelium intact may be used.)
- Two, 2 mL cryovials containing 0.5cc of RNAlater (see section 10.2.2 Collection and Handling Procedures: Biopsy for instruction on the preparation and processing of the cryovials).
  - One labeled “Normal (EOS)”
  - One labeled “Tumor (EOS)”
- Two containers of 10% formalin.
  - One labeled “Normal (EOS)”
  - One labeled “Tumor (EOS)”

**Samples obtained during surgery:** (The participant’s pre-surgical instructions, procedure preparation and recovery will be in accordance with the PO’s standard clinical practice.)

- Using a 4 mm biopsy punch or alternative method, remove a 4 mm piece of visually normal appearing mucosa adjacent to, but at least 1 cm away from, the tumor/suspicious lesion.
- Excise the tumor in accordance with normal clinical practice.

**Visually Normal Appearing Tissue:** Place mucosa side up, on a clean hard surface. Bisect into two equal size pieces with a scalpel being careful to separate the epithelium from the subcutaneous tissue. The amount of subcutaneous tissue included in the sample should be minimized.

Place one of the halves in the RNAlater cryovial labeled “Normal (EOS)”. Place the other half in a container of 10% formalin.

**Tumor Tissue:** After excision, remove a 2 mm piece of tumor for RNA-seq analysis, being careful to separate the epithelium from the subcutaneous tissue. The amount of subcutaneous tissue included in the sample should be minimized. Place this piece in the cryovial of RNAlater labeled “Tumor (EOS)”. A full 4 mm piece does not need removed as it is preferable that the remainder of the tumor be sent intact to pathology for paraffin embedding and routine clinical histopathology.

Submit the remainder of the surgically excised tissue to pathology in accordance with normal clinical practice.

Process the RNAlater samples in accordance with the instructions in section 10.2.2

Samples in formalin will be paraffin-embedded and stored en bloc until the request for slides to be cut is issued by the CLO.

**Samples obtained in the clinic** (because definitive treatment will be radiation or chemoradiation without surgical excision of the primary tumor or because surgical excision of the primary tumor has been delayed):

Obtain the tissue samples:

- Using a 4 mm biopsy punch or alternative method, remove a 4 mm piece of visually normal appearing mucosa adjacent to, but at least 1 cm away from, the tumor/suspicious lesion.
- Using a 4 mm biopsy punch or alternative method, remove a 4 mm piece of the tumor/suspicious lesion.

Using great care not to mix up the two tissue types, place each tissue sample, mucosa side up, on a clean hard surface.

**Visually Normal Appearing Tissue:** Using a scalpel, carefully separate the epithelium from the subcutaneous tissue (the amount of subcutaneous tissue included in the sample should be minimized). Cut the epithelium in half. Place one of the halves in the RNAlater cryovial labeled “Normal (EOS)”. Place the other half in a container of 10% formalin.

**Tumor Tissue:** Using a scalpel, carefully separate the epithelium from the subcutaneous tissue (the amount of subcutaneous tissue included in the sample should be minimized). Cut the epithelium in half. Place one of the halves in the RNAlater cryovial labeled “Tumor (EOS)”. Place the other half in a container of 10% formalin.

Process the RNAlater samples in accordance with the instructions in section 10.2.2

Samples in formalin will be paraffin-embedded and stored en bloc until the request for slides to be cut is issued.

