### 1.2 Secondary Objectives –

1.2.1 Compare differences in proliferation index (Ki-67) expression from baseline to post-exposure in visually normal appearing oral cavity/oropharyngeal tissue.

1.2.2. Compare immunohistochemical differences in the apoptosis biomarker Cleaved Caspase 3 from baseline to post-exposure in oral cavity/oropharyngeal adjacent visually normal appearing tissue and tumor tissue samples.

1.2.3. Compare immunohistochemical differences from baseline to post-exposure in oral cavity/oropharyngeal tumor tissue samples with regard to Cyclin D1, p21 and biguanide or PPAR $\gamma$  associated pathway biomarkers. Prospective biomarkers on the panel will include pAKT, pAMPK, pS6 (Metformin), and PPAR $\gamma$ .

1.2.4. Compare immunohistochemical differences from baseline to post-exposure of oral cavity/oropharyngeal tumor tissue samples with regard to tumor infiltrating immune cells (effector CD8 (CD8+), regulatory CD4 Treg (CD4+Foxp3+), tumor associated myeloid cells (CD68), PD1 and PD-L1.

1.2.5. Compare and correlate pre- and post-ACTOplus met® XR treatment Human RNA-seq gene analysis on total RNA samples from oral cavity/oropharyngeal adjacent visually normal appearing tissue and tumor tissue pre-and post-study treatment.

1.2.6. Determine HPV status in pre-treatment tumor tissue using p16 immunohistochemistry.

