### 2.3.2 Biguanides: Metformin:

Metformin, a first-line drug commonly used to treat diabetes mellitus, also directly inhibits cell growth. Besides inhibiting gluconeogenesis, this biguanide derivative directly activates adenosine monophosphate-activated protein kinase (AMPK) in epithelial cells by a liver kinase B1 (LKB1)-dependent mechanism. AMPK appears to be a key molecular target for cancers associated with diabetes mellitus and obesity. AMPK is an intracellular regulator that is activated when the cell senses conditions of decreased energy such as low glucose, hypoxia, or ischemia [28; 29]. AMP, which is present under conditions of starvation when adenosine triphosphatase levels are low, binds to the  $\gamma$  subunit of AMPK allowing AMPK to be activated allosterically by LKB1. Activation of AMPK increases insulin-stimulated glucose uptake. It also inhibits mammalian target of rapamycin (mTOR) via tuberous sclerosis complex 2/1, resulting in decreased protein synthesis mediated by the downregulation of the ribosomal protein S6K. Exposure of breast cancer cells to metformin decreases phosphorylated AKT and activation of mTOR, resulting in inhibition of cell proliferation and an increase in apoptosis [30]. The cell signaling pathways of adiponectin and leptin, two other hormones implicated in obesity-associated carcinogenesis may also be mediated by AMPK, but do not appear to be affected by metformin [28; 29; 31]. Metformin also has indirect anti-proliferative effects related to lower systemic levels of insulin.

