## 6. PHARMACEUTICAL INFORMATION

### 6.1 ACTOplus met® XR IND Exempt (132630)

ACTOplus met® XR (Takeda Pharmaceuticals America, Inc., Deerfield, IL) is a fixed-dose combination (FDC) drug of pioglitazone immediate-release combined with metformin extended-release. This FDC is approved as an adjunct to diet and exercise to improve glycemic control for patients with type 2 diabetes mellitus. Pioglitazone is an agonist of peroxisome proliferator-activated receptor  $\gamma$  (PPAR $\gamma$ ), a ligand-activated nuclear transcription factor belonging to the steroid receptor superfamily that is a key regulator of insulin-responsive genes involved in the control of glucose and lipid metabolism as well as adipogenic differentiation. While originally believed to be adipocyte-specific, accumulating data show that PPAR $\gamma$  is also expressed in normal liver and skeletal muscle and in neoplastic tissue, including breast, colon, prostate, and lung. PPAR $\gamma$  activation by pioglitazone in breast, colon, and lung cancer cell lines leads to differentiation and/or apoptosis [16-18; 21]. Consistent with the cell observations, mouse xenograft studies using breast and colon cancer cell lines have shown significant reduction in tumor size after treatment with pioglitazone compared with vehicle controls, with induction of apoptosis in the breast tumors [17; 18]. Pioglitazone was also effective in multiple different carcinogen-induced cancer models, such as colon, lung, and oral squamous cell carcinoma [22; 23; 25; 54].

Metformin, a first-line drug commonly used to treat diabetes mellitus, also inhibits cell growth. Besides inhibiting gluconeogenesis, this biguanide derivative indirectly activates adenosine monophosphate-activated protein kinase (AMPK) in cells by a liver kinase B1 (LKB1)-dependent mechanism. AMPK appears to be a key molecular target for cancers associated with diabetes mellitus and obesity since it is activated under conditions of decreased energy, such as low glucose, hypoxia, or ischemia [28; 29]. Activation of AMPK inhibits mammalian target of rapamycin (mTOR) via tuberous sclerosis complex 2/1. Exposure of breast cancer cells to metformin decreases phosphorylated AKT and activation of

mTOR, resulting in inhibition of cell proliferation and an increase in apoptosis [30]. Metformin also has indirect anti-proliferative effects related to lower systemic levels of insulin.

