#### **Tumor tissue from a histologically diagnosed lesion:**

Using a scalpel, carefully separate the epithelium from the subcutaneous tissue (the amount of subcutaneous tissue included in the sample should be minimized). Cut the epithelium in half. Place one of the halves in the RNAlater cryovial labeled “Tumor (Baseline)”. Place the other half in a container of 10% formalin.

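### Surgical end-of-study tumor is sampled after excision, so a within-arm change in pAMPK (and by inference pS6) cannot be attributed to the drug; the between-arm test stays unbiased but can lose power

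*Combined protocol and SAP*

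**What the plan says.** **Baseline and clinic tumor samples (7.6.1).** Tumor is taken with a 4 mm punch or an equivalent tool and divided at collection. One half goes into RNAlater; for the other, the instruction for a diagnosed lesion is "Place the other half in a container of 10% formalin". End-of-study samples taken in clinic are handled the same way.

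**Surgical end-of-study samples (7.6.1).** The first listed step is to "remove a 4 mm piece of visually normal appearing mucosa adjacent to, but at least 1 cm away from, the tumor/suspicious lesion". The next is to excise the tumor. For tumor RNA the text then reads "After excision, remove a 2 mm piece of tumor for RNA-seq analysis", and for everything else "Submit the remainder of the surgically excised tissue to pathology in accordance with normal clinical practice". Section 3 confirms that this formalin-fixed surgical tumor goes through standard histopathology, so it is the source of the end-of-study tumor IHC sections.

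**Timing.** The documents set no limit on the time from loss of blood supply or excision to RNAlater or formalin. The only holding rule, 12 to 72 hours at 4°C in Section 10.2.2, starts once tissue is already in RNAlater.

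**Biology.** Section 2.3.2 says "AMPK is an intracellular regulator that is activated when the cell senses conditions of decreased energy such as low glucose, hypoxia, or ischemia", and Section 6.1 repeats the point. Section 2.3.2 adds that AMPK inhibits mTOR, "resulting in decreased protein synthesis mediated by the downregulation of the ribosomal protein S6K".

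**Use of the markers.** Objective 1.2.3 concerns change from baseline to post-exposure in tumor: "Prospective biomarkers on the panel will include pAKT, pAMPK, pS6 (Metformin), and PPAR" gamma. Objective 1.2.5 is worded as a comparison before and after active treatment. Section 13.5 summarizes change by arm and tests it between arms, by t-test or rank-sum test. Section 8.2.4 likewise runs differential expression between treatment and control.

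**The concern.** In surgical participants the baseline and end-of-study tumor samples differ in two ways: exposure to study agent, and time without blood supply before fixation. By the protocol's own account, the second difference can raise pAMPK and, through mTOR, lower S6 signalling. Those are the directions that would be read as a metformin effect.

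Two things are at stake. The first is interpretation: objectives 1.2.3 and 1.2.5 invite a pre/post reading within the active arm, which cannot separate drug from handling. The second is precision. Some participants are sampled at surgery and some in clinic, so a handling shift present in only one group widens the spread of change scores in both arms of a trial with 24 and 12 evaluable participants.

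**Working it through.** **1. Inputs from the documents.** 24 active and 12 placebo evaluable, two-sided alpha 0.05, detectable effect 1.00 / 1.06 / 1.15 SD at power 0.80 / 0.85 / 0.90 (13.3). These figures are for Ki-67; none is given for pAMPK, pAKT, pS6 or RNA-seq. Sampling route is not a stratification factor (13.2).

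**2. Assumptions.** Surgical share s = 0.5 to 0.9. Handling shift k = 0.5 to 2 SD of the change score, the same in both arms.

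**3. The plan's own figure.** Effective n per arm = 1/{[1/24 + 1/12]/2} = 16, and d = (z for alpha + z for power) × √(2/16):
- power 0.80: (1.960 + 0.842) × 0.3536 = 0.991
- power 0.85: (1.960 + 1.036) × 0.3536 = 1.059
- power 0.90: (1.960 + 1.282) × 0.3536 = 1.146

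These reproduce the stated values. The exact t calculation at 24:12 gives 1.02 / 1.09 / 1.18. For a 1.00 SD effect the noncentrality is 1/√(1/24 + 1/12) = 2.828 on 34 df, and exact power is 0.785. That is the reference below.

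**4. Within one arm.** Spurious mean change = s × k, from 0.5 × 0.5 = 0.25 SD to 0.9 × 2 = 1.8 SD. In simulation (40,000 trials per setting, no drug effect, s = 0.7, k = 1), a pre/post test is significant in 84% of active arms and 52% of placebo arms.

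**5. Between arms, bias.** Expected difference = (drug effect + s × k) − (s × k) = drug effect. In the same simulation the between-arm test rejects in 5.1% of trials. Over s = 0.5 to 1.0 and k = 0.5 to 1.5, it rejects in 4.7% to 5.1%, with mean bias about zero.

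**6. Between arms, power.** The variance of change becomes 1 + s(1 − s)k², so a true 1.00 SD effect shrinks to 1/√(1 + s(1 − s)k²).

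| s | k | Effective effect (SD) | Power |
|---|---|---|---|
| any | 0 | 1.00 | 0.785 |
| 0.9 | 0.5 | 1/√1.0225 = 0.99 | 0.78 |
| 0.9 | 1 | 1/√1.09 = 0.96 | 0.749 |
| 0.7 | 1 | 1/√1.21 = 0.91 | 0.705 |
| 0.5 | 1 | 1/√1.25 = 0.89 | 0.691 |
| 0.5 | 2 | 1/√2 = 0.71 | 0.493 |

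If every participant is sampled at surgery, s(1 − s) = 0 and no power is lost to mixing.

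**7. Adjusting for route.** With sampling route as a covariate, simulated power at s = 0.7, k = 1 rises from 0.70 to 0.77. With no shift, the covariate costs about 0.01.

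**The case against.** The strongest reply is that the planned analysis already protects against this. Sections 13.5 and 8.2.4 test between randomized arms, placebo surgical participants are sampled the same way, and within-arm change is only described. That stands. A reader might infer that handling could by itself produce a treatment difference; step 5 shows that it does not.

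The power loss rests on two quantities absent from the documents, and 0.49 is the worst corner of the assumed range. The 1.00 SD benchmark belongs to Ki-67, so no stated operating characteristic is broken. That also stands.

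Other stronger readings fail on the text. The documents link ischemia to AMPK and, through mTOR, to S6K. They state no ischemia effect on pAKT, the transcriptome or Ki-67, nor how fast or how far pAMPK shifts in excised tissue. Masking of a drug effect at a marker ceiling has no figure behind it. A confounded tumor-versus-normal RNA contrast is not established either: the normal punch is listed before excision, but its division and transfer to RNAlater carry no timing, and Section 13.5 specifies no such test.

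Sampling after excision is also deliberate, since 7.6.1 prefers an intact specimen for pathology. Requiring a pre-excision tumor punch would be a debatable trade-off. Finally, the visit worksheets (12.3) are not in the documents and might capture times; what can be said is that the protocol does not require them.

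What survives is the within-arm confounding for pAMPK, the inference for pS6, and the avoidable variance.

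**Conclusion.** The point holds in limited form. Within either arm, a baseline-to-post change in tumor pAMPK, and by inference pS6, cannot be attributed to the drug, because surgical end-of-study tissue is handled differently from baseline in a way the protocol itself says activates AMPK. The spurious change would be 0.25 to 1.8 SD under the assumed ranges. For pAKT, the other tumor markers and RNA, the documents support only a precaution.

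The between-arm comparison is valid. Its possible loss is precision: power for a 1.00 SD effect of between 0.49 and 0.78, against 0.785 with uniform sampling, for an assumed 50-90% surgical share and 0.5-2 SD shift. These are secondary endpoints in a study that Section 13.5 calls exploratory, so this is a worthwhile and cheap improvement, not a flaw in the primary analysis.

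**What to change.** 1. **Section 7.6.1:** for every end-of-study tumor sample, record the time of excision (or biopsy) and the time into RNAlater or formalin. This costs a few data fields and has to be done prospectively, since unrecorded times may not be recoverable.
2. **Section 13.5:** compare change in pAMPK, pS6, the other tumor markers and RNA between arms with sampling route (surgery versus clinic) as a covariate. This costs one degree of freedom. Use a covariate, not separate stratum results: at 90% surgical, only about 12 × 0.1 = 1.2 placebo participants would be sampled in clinic.
3. **Objectives 1.2.3 and 1.2.5, and Section 13.5:** state that conclusions rest on the between-arm contrast, with pre/post change within the active arm reported descriptively.
4. **Reconcile the sampling text.** Section 7.4.7, the opening of the end-of-study part of 7.6.1, and Section 10.2.2 call for 4 mm samples of tumor and normal tissue, with 7.6.1 sending half of each to RNA-seq and half to formalin. Section 3, footnote 6 to the schedule in 7.1, and the surgical tumor paragraph of 7.6.1 describe a 2 mm tumor piece, which 7.6.1 takes after excision with the remainder going intact to pathology.

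A tumor punch before excision can be offered as an option where the surgeon and pathologist agree. Section 15 already covers added costs of collecting the tumor sample during surgery.

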#### 7.6.2 PET-CT

If the participant had a staging FDG-PET/CT as part of their standard clinical care upon diagnosis, they are asked to have the scan repeated for research purposes. This will be a skull base to thigh FDG-PET/CT performed prior to the collection of the end of study tissue biopsies. The scan will be performed as close to the day of tissue sample collection as possible (ideally the same day or one day before) but if the scan must be performed earlier than this due to scheduling constraints, the participant must have completed a minimum of 10 days of study agent dosing prior to the scan. The preparation for, performance of, and post-procedure participant instructions will be in accordance with the institution’s standard clinical practice.

The request will be made that the tumor burden be assessed using RECIST (Response Evaluation Criteria in Solid Tumors) 1.1. [56] Tumor lesions will be measured in at least one dimension – the longest diameter in the plane of measurement. Any lymph nodes  $\geq 15$  mm in the short axis will be measured bi-dimensionally and reported. If the participant’s standard of care staging FDG-PET/CT to be used as the baseline scan was performed at an outside institution, a copy of that scan will be obtained and provided to the radiologist performing the end of study scan. If the baseline scan results were not reported using RECIST, the radiologist will be requested to re-read the baseline scan using RECIST criteria.

For the exploratory endpoint analysis, a maximum of 5 target lesions will be identified on the baseline scan using RECIST criteria. Target lesions will be identified by type (primary lesion or secondary lesion) and anatomic location (oral cavity, oropharynx, other body organ, lymph node etc.).

Primary lesion: the primary tumor from which the baseline tumor tissue sample was collected.

Secondary lesions: may be a tumor lesion (i.e. a lesion in a body organ) or a malignant lymph node.

- To meet target criteria, a secondary tumor lesion must be  $\geq 10$  mm in size. No more than 2 target lesions may be identified per organ. For example, if there is more than one lesion appearing in the oral cavity/ oropharynx, the primary lesion and the next largest lesion will be the only two identified as “target” lesions.
- To meet target criteria, a lymph node must have a short axis  $\geq 15$  mm.

The following will be reported and documented on each of the “target” lesions identified:

- SUV (Standardized Uptake Value) of FDG
- Tumor burden:
  - For tumor lesions, document the length (in mm) of the longest diameter in the plane of measurement.
  - For lymph nodes, document the length (in mm) of the short axis. For example, a lymph node measuring 17 mm x 24 mm would be documented as 17 mm.

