physical exam was done but did not assess for one of the required elements (ECOG performance status, edema, signs/symptoms of congestive heart failure, HEENT, Chest, Heart or Abdomen) only those required elements not assessed need to be performed]. Copies of blood test results must contain the lab's reference (normal) range for the test.

- Medical/Surgical History and Concomitant Medication assessment
- Baseline symptoms
- ECOG performance status
- Eligibility Questionnaire
- Physical Exam, height, weight and vital signs
- Clinical lab tests: CBC with differential, Comprehensive Metabolic Panel and urine pregnancy test (for women of childbearing potential)
- Baseline tobacco and alcohol use assessments

A blood sample for baseline PK analysis will also be obtained.

Patients who meet the eligibility criteria for the protocol will have baseline tissue samples for biomarker analysis obtained in clinic or in conjunction with a standard of care direct operative laryngoscopy with biopsy (DL biopsy) performed for diagnostic purposes. Two 4 mm biopsies: one of tumor and one of adjacent normal appearing tissue will be obtained. Half of each biopsy will be placed in RNA later. The other half will be formalin-fixed and paraffin-embedded. For those participants with an undiagnosed suspicious lesion, the paraffin-embedded biopsy sample from the lesion will be submitted for pathology review.

Patients with undiagnosed suspicious lesions will not be randomized until they have a histologically confirmed cancer, and a treatment plan is established. (If the presence of cancer is not confirmed, the patient will be considered a screen failure.)

If a standard of care staging PET/CT is planned, the participant's randomization will be held until the scan is completed. The results will be documented and used in an exploratory analysis of the effect of study agent on FDG uptake and tumor burden (per RECIST v 1.1 criteria). This exploratory analysis will be performed only on those participants who have had a standard of care staging PET/CT. A staging scan is not a required baseline assessment. Those participants who have had a standard of care staging PET/CT will be asked to have a repeat scan, for research purposes only, conducted prior to the collection of their end of study tissue samples in order to complete the exploratory analysis.

Confirmation of eligibility and randomization will be performed by the Contract Lead Organization (CLO).

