13.5.7 In those participants who have had a standard of care staging PET/CT prior to randomization, we will compare the pre- and post-study intervention: SUV (Standardized Uptake Value) of FDG and tumor burden using RECIST v 1.1 between the two treatment arms. Because only a subset of participants will have PET/CT scans performed, this will be an exploratory analysis.

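### The baseline PET/CT is re-read only if it was not reported by RECIST, so for the other scans the two halves of a pre/post pair can come from different readers

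*Combined protocol and SAP*

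**What the plan says.** The PET/CT analysis is exploratory and limited to participants with a standard of care staging scan (1.3.1, 3, 13.5.7). Section 3 says of the staging scan: "The results will be documented and used in an exploratory analysis of the effect of study agent on FDG uptake and tumor burden".

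Section 7.6.2 deals with the reading of the two scans:

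- For a baseline scan done at an outside institution, "a copy of that scan will be obtained and provided to the radiologist performing the end of study scan".
- On re-reading: "If the baseline scan results were not reported using RECIST, the radiologist will be requested to re-read the baseline scan using RECIST criteria".
- On lesion selection, for the exploratory analysis, "a maximum of 5 target lesions will be identified on the baseline scan using RECIST criteria". The primary lesion is defined as "the primary tumor from which the baseline tumor tissue sample was collected". Limits follow for lesions per organ, secondary lesions and nodes.
- On recording: "The following will be reported and documented on each of the" target lesions. The list then gives "SUV (Standardized Uptake Value) of FDG" and, as a separate item, tumor burden.

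Section 13.5.7 uses these values: "we will compare the pre- and post-study intervention: SUV (Standardized Uptake Value) of FDG and tumor burden" between the two arms.

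**The concern.** A pre/post change is cleanest when the same lesions are measured in the same way at both times. Whether the clinical report used RECIST does not settle that. It says nothing about who read the scan, and nothing about whether SUV was recorded for each target lesion, since the protocol lists SUV separately from RECIST tumor burden.

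The condition therefore splits the PET/CT subset in two. Where the baseline was not reported by RECIST, the re-read brings both scans to one radiologist, if the request is met. Where it was reported by RECIST, nothing in the plan does so, and the change may include a difference between readers.

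What is at stake is the precision of an exploratory comparison, and possibly the loss of some SUV pairs, in a small trial. Section 13.3 plans 39 participants (26 active, 13 placebo), and only part of them will have PET/CT.

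**Working it through.** **Text check.** The documents give no sample size, power, expected change or measurement error for the PET/CT analysis, so there is no figure of the plan to reproduce. The question is whether any provision brings both scans to one reader.

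1. *Re-read request (7.6.2).* It is conditional on the absence of a RECIST report and on nothing else. It is also worded as a request.
2. *Outside scans (7.6.2).* The images go to the radiologist of the end-of-study scan, however they were reported. That makes a paired read possible but does not require one.
3. *Target-lesion and SUV rules (7.6.2).* They apply to every PET/CT participant, with no exception for scans already reported by RECIST. They do not say who applies them, or what happens if an existing report lists other targets or gives no SUV per lesion.
4. *Elsewhere (1.3.1, 3, 7.1, 7.4.1, 13.5.7).* There is no central read, paired read or single-reader requirement. Section 3 has the staging results documented and used.

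So for a scan already reported by RECIST, the plan sets a requirement (targets and SUV by the 7.6.2 rules) but assigns no one to meet it, and the baseline measurements may remain the original reader's.

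**Illustration of size.** The inputs are assumptions and do not come from the documents: within-reader SD *sw* of 5-10% and between-reader SD *sb* of 5-15%. A reader's offset is taken to be the same on both scans, so it cancels when one person reads both.

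- One reader: SD of a change = √(2·sw²).
- Two readers: SD of a change = √(2·sw² + 2·sb²).
- Ratio of measurement variances: R = 1 + (sb/sw)².

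| sw | sb | SD, one reader | SD, two readers | R |
|---|---|---|---|---|
| 10% | 5% | √200 = 14.1% | √250 = 15.8% | 1.25 |
| 5% | 5% | √50 = 7.1% | √100 = 10.0% | 2.0 |
| 10% | 15% | √200 = 14.1% | √650 = 25.5% | 3.25 |
| 5% | 15% | √50 = 7.1% | √500 = 22.4% | 10 |

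The four rows are the corners of the assumed ranges, so R lies between 1.25 and 10.

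Two limits apply. R covers measurement variance only. True variation between participants in the change adds equally to both cases, so the ratio for the observed change is smaller than R. And R applies only to pairs read by two people. If a share *p* of pairs is affected, the average measurement variance rises by the factor 1 + p(R − 1), which is 1 when p = 0 and R when p = 1. The documents do not give p.

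**The case against.** The strongest reply is that 7.6.2 already covers the substance. Directly after the re-read sentence it sets one selection rule on the baseline scan for everyone in the analysis, and it requires SUV and size for each target. A reader might infer from the conditional sentence that the plan allows different lesion sets at the two times, or allows baseline SUV to be absent. The documents do not support that: no line lets a clinical report override the target rules or the SUV requirement, and the summary in section 3 does not cancel them. Different lesions and missing SUV are risks of execution. What remains is that no reader is named, and that a missing SUV does not prompt a re-read.

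A second reply is that the affected group may be very small or empty. It needs a staging scan already reported by RECIST and a different person reading the follow-up. The documents do not say how often that happens. This stands, and it limits the importance of the point.

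A third reply is that the trial is randomized and double-blind (6.9, 13.2), so reader differences should mainly add noise to the comparison of arms. This stands too. A reader might infer a biased treatment comparison, but nothing in the documents links the re-read condition to treatment arm. Pre/post summaries within an arm are more exposed, because there a systematic reader difference does not cancel.

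**Conclusion.** The point holds as a narrow one. The re-read condition does not ensure that the two scans of a pair have the same reader, and scans already reported by RECIST are the ones left out. The consequence is extra measurement variance for those pairs, by a factor of 1.25 to 10 under the assumed SDs, in an exploratory subset analysis. The textual finding does not depend on those SDs; the factor does, and it also needs reader offsets that stay constant across scans.

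It would be tempting to say that reader noise could hide any drug effect over 10-21 days. The documents do not support this, because they give neither an expected change in SUV or size nor a measurement error to set against it. The primary Ki-67 analysis is untouched. This is a cheap improvement, not a fault in the trial's main inference.

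**What to change.** In 7.6.2, replace the conditional re-read sentence with:

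> The radiologist who reads the end-of-study scan will also re-read the baseline scan of every PET/CT participant, whether or not it was reported using RECIST, will apply the target-lesion rules below to the baseline images, and will record size and SUV of the same target lesions on both scans; these values are used in 13.5.7.

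This names the reader, makes the re-read unconditional, and means a missing SUV in the clinical report no longer matters. It needs no new scan, visit or reader: that radiologist already reads the end-of-study scan and already receives outside baseline images. The cost is reading time for baseline scans that already have a RECIST report. No additional analysis is needed in section 13.
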